2.3.2 Potential Benefits

This study will provide mechanistic insight into the underlying causes and molecular level pathogenesis of periodontal diseases. We will identify key mechanisms that potentially confer risk and protection. Ultimately this may lead to new and improved diagnostics and therapeutics. Since IFI16 and AIM2 are reported to be involved in other diseases, clarifying the role of these proteins in periodontal disease will also provide insights into the role of these proteins in other inflammatory conditions.

Orally healthy individuals will receive adult prophylaxis that is recommended for healthy individuals every 6 months. Subjects with periodontal conditions will have therapeutic benefit from the treatment. Diseased subjects will be offered referral to the UNC School of Dentistry graduate clinics for additional care at reduced fees, based upon the UNC School of Dentistry graduate student fee schedule, to treat their periodontal condition beyond initial periodontal therapy.

3 OBJECTIVES

3.1 Study Objectives

We will establish 2 new cohorts of individuals: healthy with acute inflammation (SIBO) and chronic periodontitis with acute inflammation (SIBO) to study the role of IFI16 and AIM2 in the pathogenesis of periodontitis. Studying these proteins individually and collectively, along with upstream and downstream events, will yield to new approaches to potentially treat periodontal disease severity and progression. This project will form the basis of a future project involving inflammasomes and alternative therapeutic approaches. The study objectives are to:

1) (Primary) compare the expression of AIM2 and IFI16 between healthy (PPC-A, PPC-B) and severe periodontitis (PPC-E, PPC-G) subjects during an acute inflammatory response using the stent-induced biofilm overgrowth model (SIBO).

2) (Exploratory) correlate the expression of these proteins with periodontal pathogens

3.2 Study Outcome Measures

Primary study outcomes measured for individuals in each group (healthy and severe periodontitis):

- Expression of AIM2 and IFI16 levels will be quantified by IHC and qRT-PCR
- Periodontal clinical measurements
- Composition of oral microbiota by 16S rDNA (Illumina)

4 STUDY DESIGN

A total of 72 subjects will be enrolled. Specifically, a sufficient number of adults 18 years and older will be screened until 36 healthy (PPC-A, PPC-B) subjects and 36 subjects with severe periodontal disease (PPC-E, PPC-G) will be enrolled based on the algorithm previously defined on Morelli et al. 2017. Eligibility for study participation will be determined during the screening session. Barring dropout, subject participation will include 1 to 8 visits lasting over a maximum period of 56 days. The last 3 visits (visit 5-8) will depend on the individual need of the subject for providing SRP. Clinical data and medical history data will be collected at the screening visit to ascertain eligibility. All subjects will have dental plaque and a gingival biopsy collected at baseline. Enrolled subjects will be included in an experimental gingivitis model (SIBO) for 21 days. Individuals will return for safety checks every week during the 21-day period. At 21-days, plaque samples and a gingival biopsy will be collected. For individuals with severe periodontal disease, SRP will initiate during the 21-day visit at the SIBO quadrant. Visit 6 (28 days) will include the post-biopsy follow up, prophylaxis (for healthy individuals) and SRP (diseased individuals). Subjects receiving SRP may have 2 additional visits (visit 7 at day 35 and visit 8 at day 42) for completing the SRP of all quadrants and will be dependent on individual need. Medical histories, demographics, height and weight, clinical and biological data described above will be recorded and stored on a secure server located at the University of North Carolina. Each participant enrolled into the study will have a unique identification number that has been stripped of any information that could be used by non-study members to identify the subject.

5 STUDY ENROLLMENT AND WITHDRAWAL

All subjects will be seen in the General and Oral Health Center, which is a dental research clinic at the University of North Carolina at Chapel Hill School of Dentistry. The General and Oral Health Center is affiliated with the UNC CTSA. There are no collaborating sites where human subject's research will be performed.

5.1 Subject Inclusion Criteria

In order to be eligible to participate in this study, an individual must meet all of the following criteria:

- Subjects must have read, understood and signed an informed consent form.
- Subjects must be able and willing to follow study procedures and instructions.
- Subjects must be adult males or females with a minimum of 18 years (inclusive).
- Subjects must present with at least 20 teeth in the functional dentition, excluding third molars.
- Subjects must have at least 2 natural adjacent teeth in two posterior sextants that will be selected for baseline gingival biopsy and SIBO gingival biopsy.
- Subjects must be in good general health, as evidenced by medical hx (exclusion conditions defined under subject exclusion criteria below).
- Females of child-bearing capacity must be willing to have pregnancy test to confirm they are not pregnant.
- Subjects must be in the healthy (PPC-A, PPC-B) or severe periodontitis (PPC-E, PPC-G) categories according to the PPC (1).

5.2 Subject Exclusion Criteria

An individual who meets any of the following criteria will be excluded from participation in this study:

- If the sextants identified for the analysis has implants
- All individuals who meet criteria for anti-infective prophylaxis prior to dental procedures should be excluded from this study.
- Chronic disease with oral manifestations including diabetes mellitus.
- Current smoker or one that has stopped smoking less than 2 years prior to enrollment (self-report).
- Gross oral pathology other than the periodontal disease.

- Treatment with antibiotics for any medical or dental condition within 1 month prior to the screening examination.
- Chronic treatment (i.e., two weeks or more) with any medication known to affect periodontal status (e.g., phenytoin, calcium antagonists, cyclosporin, coumadin, non-steroidal anti-inflammatory drugs, aspirin) within one month of the screening examination.
- Ongoing medications initiated less than three months prior to enrollment (i.e., medications for chronic medical conditions must be initiated at least three months prior to enrollment).
- Significant organ disease including impaired renal function, heart murmur, history of rheumatic fever or valvular disease, or any bleeding disorder.
- Individuals with prosthetic material used for intra-cardiac repair (e.g. for congenital heart disease), or intra-cardiac devices, cardiac transplant, infective endocarditis and individuals who have had previous infectious complications of prosthetic joint infections
- Infectious diseases such as hepatitis, HIV or tuberculosis.
- Anemia or other blood dyscrasias.
- Anticoagulant therapy or drugs, such as heparin or warfarin.
- Severe unrestored caries, or any condition that is likely to require antibiotic treatment over the trial.
- Pregnant, or expect to become pregnant within the next several months.
- Females of child-bearing capacity not using any form of contraceptive methods
- Anything that would place the individual at increased risk or preclude the individual's full compliance with or completion of the study.

5.3 Strategies for Recruitment and Retention

Before initiation of the study, the investigator will obtain written approval of the research protocol and informed consent form from the UNC IRB complying with the provisions specified in 21 CFR Part 56 and applicable pertinent governmental regulations.

All recruitment plans including advertising, email postings, and flyers will be submitted to the IRB and must be approved before study initiation. Our plan is to use campus-wide list server postings, website postings, our IRB approved patient registry, newspaper ads and postings within UNC including the dental school and the local community. Our dental school has a lottery-based patient acceptance program and many individuals are on waiting lists to become patients within the dental school clinics. While waiting to be accepted at the dental school, subjects become patients of the General and Oral Health

Center and are able to receive dental care per study protocol as well as referrals to other dental clinics within the school as appropriate.

Monetary compensation of \$200 after completion of 2 biopsy procedures will be provided at the end of visit 5. Free parking vouchers will be given to each subject for every completed visit. Periodontal treatment that includes scaling and root planning may be offered to each study participant according to his/her level of need. Study participants will be called by phone and/or emailed, depending upon their indicated preferred contact method, to be reminded of planned study visits or to reschedule missed study visits.

5.4 Subject Withdrawal

Subjects may withdraw from the study at any time at their own request, or they may be withdrawn at any time at the discretion of the Investigator for safety, behavioral or administrative reasons (i.e. protocol compliance). If a participant withdraws consent, no further evaluations will be performed on that participant and no attempts will be made to collect additional data regarding that participant. If a participant fails to present for a scheduled study visit, study staff will attempt three times to reschedule the participant utilizing the means of contact provided by the participant.

5.4.1 Reasons for Withdrawal

The Investigator may discontinue a subject if, in the opinion of the Investigator, the subject is no longer a suitable candidate for the study.

Possible reasons for the discontinuation of a subject are including but not limited to:

- ✓ Adverse events (i.e. delayed healing)
- ✓ Protocol deviations (i.e. subject compliance with protocol)
- ✓ Failure to meet or maintain eligibility

5.4.2 Handling of Subject Withdrawals

All participants that prematurely discontinue from the study, regardless of cause will be given the opportunity to be seen for a final evaluation and complete a dental prophylaxis. Withdrawn subjects with unresolved oral disease will be offered referral for dental care within the UNC School of Dentistry. Subjects will only be compensated after two biopsy procedures are completed.

Any participant with an AE that is ongoing at the time of discontinuation will be followed until the event returns to baseline, resolves, or stabilizes. If the AE does not meet these outcomes within 30 days after discontinuation, the participant will be offered a referral to an appropriate practitioner for continued care.

5.5 Premature Termination or Suspension of Study

This study may be suspended or prematurely terminated if there is sufficient reasonable cause. Written notification, documenting the reason for study suspension or termination, will be provided by the suspending or terminating party. If the study is prematurely terminated or suspended, the principal investigator will promptly inform the IRB and will provide the reason(s) for suspension or termination. No interim analyses will be done to determine futility. It is expected that valuable results will be obtained from the 200 participants in the five-week SIBO experiment even if there is an unanticipated finding that no biomarkers vary across the four groups under strong error rate control. Therefore, futility analyses for potential early stopping of the trial are not applicable.

Circumstances that may warrant termination include, but are not limited to:

- ✓ Determination of unexpected, significant, or unacceptable risk to subjects.
- ✓ Insufficient adherence to protocol requirements.

6 STUDY SCHEDULE

6.1 Visit 1: Screening/enrollment

(Day -28 +/- 2 days)

- Informed Consent: Before recruitment and enrollment, each prospective candidate will be given a full explanation of the study, and allowed to read the informed consent form that has been approved by the Institutional Review Board. Qualified study personnel will directly ask the subject if he/she understands the implications of participating in the study. Subject will have the opportunity to ask questions and have answers related to the study participation. No protocol procedures will be performed prior to confirmation that the subject understands the procedures and risks. Once the subject confirms this understanding verbally, the subject will be asked to give consent to participate in the study by signing the informed consent form. The study personnel will provide copies of the signed informed consent forms to the subject.
- Study personnel will obtain medical history and demographics related to the participant, height and weight
- Study personnel will record the subject's vital signs (blood pressure and pulse).
- Female participants capable of child bearing will be given a urine-based pregnancy test.
- A dental examiner (calibrated dentist or dental hygienist) will perform an intraoral examination to verify no presence of oral pathology.
- Dental examiner will perform a comprehensive periodontal screening examination that includes Plaque Index (PI), Gingival Index (GI), Pocket Depth (PD), Bleeding on Probing (BOP) and Clinical Attachment Levels (CAL).
- Subjects in the categories of healthy (PPC-A, PPC-B) or severe disease (PPC-E, PPC-G) will be considered eligible for the study.
- If the participant meets eligibility criteria during the clinic visit, the participant will be invited to participate in the research study at that time. If determined non-eligible, the individual will be informed at that visit, or by telephone, to avoid an unnecessary visit. All subjects that complete visit 1 will receive a free parking voucher.
- If eligible, an alginate impression will be taken for stent fabrication

- The interproximal region of a tooth will be selected by a dental examiner for the first gingival biopsy (occurs at visit 2).
- The subject will receive a parking voucher for the Dogwood deck and be scheduled for visit 2

6.2 Visit 2: Baseline

(Day 0 +/- 5 days)

- Study personnel will update medical history, including concomitant medication, enquire about potential adverse events related to the dental exam performed during screening and ask continuance criteria questions.
- Study personnel will record the subject's vital signs (blood pressure and pulse).
- A dental examiner will verify the previously performed intraoral exam and assess for potential adverse events.
- Dental examiner will perform a comprehensive periodontal screening examination that includes Plaque Index (PI), Gingival Index (GI), Pocket Depth (PD), Bleeding on Probing (BOP) and Clinical Attachment Levels (CAL).
- The dental examiner will collect two separate subgingival plaque samples from the interdental sulcus of the teeth that are selected for a gingival biopsy (see appendix II). Dental implant sites will not be considered for subgingival plaque samples.
- A small gingival tissue biopsy sample will be removed from underneath the papillae, buccally and lingually, to include the col area of depth of the osseous crest. Biopsies will be collected by a study dentist and performed under local anesthesia. Absorbable sutures will be used to close the interproximal papillae.
- The dental examiner will deliver 1 customized acrylic stent that will be used in a different sextant from the one that the biopsy was performed. The sextant selected will be the right posterior sextant (maxillary or mandibular), except when fewer than two teeth are present and adjacent without significant diastema.
- The participant will be instructed to defer oral hygiene measures in the experimental sextant, to wear the customized stents during brushing and to discontinue flossing throughout his/her mouth. The participant will continue to use his/her standard toothpaste and toothbrush. Participants will be informed to avoid crunchy or sticky food (e.g. apples and carrots), and use of mouthwashes during baseline through visit 5 (Day 21).
- Subjects will be monitored for safety every week during the induction of experimental biofilm overgrowth through 21 days. Any site undergoing CAL

increase of >2 mm from the baseline measurement will be deemed as “progressing.” That site will not be included in data analysis, and will receive scaling and root planing treatment as a rescue therapy.

- Subjects will be given parking vouchers for the UNC Dogwood parking deck and scheduled to return for visit 3.

6.3 Visit 3

(Day 7 +/- 5 days)

Visit 3 may occur within 7 days of visit 2 (+/-5 days). The following procedures will be performed:

- Study personnel will update medical history, including concomitant medication, enquire about potential adverse events related to the dental procedures and ask continuance criteria questions.
- Study personnel will record the subject’s vital signs (blood pressure and pulse).
- A dental examiner will verify the previously performed intraoral exam and assess for potential adverse events.
- Dental examiner will perform a comprehensive periodontal screening examination that includes Plaque Index (PI), Gingival Index (GI), Pocket Depth (PD), Bleeding on Probing (BOP) and Clinical Attachment Levels (CAL).
- A follow-up for verifying the healing of the gingival biopsy will be completed.
- The participant will be re-instructed to defer oral hygiene measures in the selected sextant and to continue wearing the customized stents during brushing of the non-selected sextants.
- Adverse events will be monitored and recorded as necessary.
- The subject will be given a parking voucher for the Dogwood deck, and Visit 4 will be scheduled.

6.4 Visit 4

(Day 14 +/- 5 days)

Visit 4 may occur within 7 days +/-5 days of day 7. The following procedures will be performed:

- Study personnel will update medical history, including concomitant medication, enquire about potential adverse events related to the dental procedures and ask continuance criteria questions.
- Study personnel will record the subject’s vital signs (blood pressure and pulse).

- A dental examiner will verify the previously performed intraoral exam and assess for potential adverse events.
- Dental examiner will perform a comprehensive periodontal screening examination that includes Plaque Index (PI), Gingival Index (GI), Pocket Depth (PD), Bleeding on Probing (BOP) and Clinical Attachment Levels (CAL).
- The participant will be re-instructed to defer oral hygiene measures in the selected sextant and to continue wearing the customized stents during brushing of the non-selected sextants.
- Adverse events will be monitored and recorded as necessary.
- The subject will receive a parking voucher to the Dogwood parking deck, and Visit 5 will be scheduled.

6.5 Visit 5

(Day 21 +/- 5 days)

Visit 5 may occur within 7 days +/-5 days of day 14. The following procedures will be performed:

- Study personnel will update medical history, including concomitant medication, enquire about potential adverse events related to the dental procedures and ask continuance criteria questions.
- Study personnel will record the subject's vital signs (blood pressure and pulse).
- A dental examiner will verify the previously performed intraoral exam and assess for potential adverse events.
- Dental examiner will perform a comprehensive periodontal screening examination that includes Plaque Index (PI), Gingival Index (GI), Pocket Depth (PD), Bleeding on Probing (BOP) and Clinical Attachment Levels (CAL).
- The dental examiner will collect two separate subgingival plaque samples from the interdental sulcus of the teeth that are selected for a gingival biopsy (see appendix II). Dental implant sites will not be considered for subgingival plaque samples.
- A small tissue biopsy sample will be removed from underneath the papillae, buccally and lingually, to include the col area of depth of the osseous crest of a tooth included in the SIBO model. The site for biopsy will be selected based on the tooth (included in the SIBO model) with the highest GI score. The biopsy will be collected by a study dentist and performed under local anesthesia. Absorbable sutures will be used to close the interproximal papillae.

- SRP may be initiated in individuals with severe periodontitis and will include the quadrant that received the gingival biopsy to allow optimal healing
- Adverse events will be monitored and recorded as necessary
- The subject will receive compensation for study participation, a parking voucher to the Dogwood deck. and visit 6 will be scheduled.

6.6 Visit 6: Final Visit (Post-biopsy follow-up; Prophylaxis; SRP may be completed up to visit 8 based on individual needs)

(Day 28 +/- 5 days)

Participants will be seen for a final visit at day 28 (+/-5 days). The following procedures will be performed at this visit:

- Study personnel will update medical history, including concomitant medication, enquire about potential adverse events related to the dental procedures and ask continuance criteria questions.
- Study personnel will record the subject's vital signs (blood pressure and pulse).
- A dental examiner will verify the previously performed intraoral exam and assess for potential adverse events.
- Dental examiner will perform a comprehensive periodontal screening examination that includes Plaque Index (PI), Gingival Index (GI), Pocket Depth (PD), Bleeding on Probing (BOP) and Clinical Attachment Levels (CAL).
- A follow-up for verifying the healing of the gingival biopsy will be done
- Prophylaxis will be performed on healthy individuals and prophylaxis/SRP will be performed on individuals with severe periodontal disease where the need is clinically indicated. Participants will be compensated for their participation in the study.
- Adverse events will be monitored and recorded as necessary.

Scaling and root planing may involve up to 2 additional visits (visit 7 and 8) that must be completed within 4 weeks of visit 6 (+/-5 days)

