11.3 Final Analysis Plan

1) (Primary) compare the expression (fold-change relative to baseline) of AIM2 and IFI16 between healthy (PPC-A, PPC-B) and severe periodontitis (PPC-E, PPC-G) subjects during an acute inflammatory response using the stent-induced biofilm overgrowth model

3) (Exploratory) correlate the expression of these proteins with periodontal pathogens

For the primary hypotheses involving gingival tissue samples, univariate and multivariate nonparametric testing procedures for SIBO experiments (Preisser, Sen and Offenbacher, 2011) will be utilized. In particular, a multivariate Wilcoxon Signed Rank test will use all available data to jointly test for changes in AIM2 and IFI16 expression levels over time (visit 2 to visit 5). If the overall multivariate test is statistically significant at the 0.05 level, then univariate Wilcoxon Signed Rank tests will be applied to AIM2 and IFI16 proteins individually. Similar procedures will be applied for expression levels from mRNA and from immunohistochemistry. Additionally, multivariate and univariate Wilcoxon Rank Sum Tests will be applied at the 0.05 significance level to compare SIBO-induced temporal change in Aim2 and IFI16 expression levels between healthy and severe periodontitis subjects.

Parametric statistical procedures will be used to summarize and test periodontal clinical measurements related to secondary hypotheses. Means and their 95% confidence intervals will be used to summarize measurements at each time point in healthy and severe periodontitis subjects. As these measurements will be collected at visits 2, 3, 4 and 5, linear mixed models will be used to assess change over time within groups and differences in change over time between healthy and severe periodontitis groups.

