Appendix II: Gingival biopsy

Strategy:

During visit (baseline, 0 day), one biopsy sample will be collected from the posterior interproximal unit determined by the dental provider. Sites will not be standardized since dentition will vary from subject to subject.

During visit 5 (day 21 of SIBO), one biopsy sample will be collected from the posterior interproximal unit in SIBO, determined by the dental provider. Sites will not be standardized since dentition will vary from subject to subject.

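### The stent sextant (right posterior by default) and the baseline biopsy sextant are set by non-random rules, so a systematic sextant difference cannot be told apart from SIBO change in hypotheses 1a and 1b

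*Combined protocol and SAP*

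**What the plan says.** Five parts of the protocol determine where the two tissue samples come from.

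- **Baseline site (6.1).** "The interproximal region of a tooth will be selected by a dental examiner for the first gingival biopsy". No rule for the choice is given.
- **Stent sextant (6.2).** The stent "will be used in a different sextant from the one that the biopsy was performed". The default is the right side: "The sextant selected will be the right posterior sextant (maxillary or mandibular), except when fewer than two teeth are present and adjacent". Either arch is allowed.
- **Visit 5 site (6.5).** "The site for biopsy will be selected based on the tooth (included in the SIBO model) with the highest GI score".
- **Appendix II.** At both visits the dental provider determines the site. "Sites will not be standardized since dentition will vary from subject to subject".
- **Eligibility (5.1).** Every subject must already have two adjacent natural teeth in each of two posterior sextants, one sextant per biopsy.

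For 1a and 1b, section 11.3 says "a multivariate Wilcoxon Signed Rank test will use all available data to jointly test for changes in AIM2 and IFI16 expression levels over time", that is, from visit 2 to visit 5. Hypotheses 1c and 1d compare that change between groups by rank sum tests. Sections 6.1, 6.2 and 11.3 contain no randomisation of sextants and no adjustment for side, arch or site. Sections 6.2 and 6.5 take plaque at the biopsied teeth, so the plaque pairs come from the same two places.

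**The concern.** Hypotheses 1a and 1b attribute the visit 2 to visit 5 difference to SIBO. The signed-rank test needs paired differences that are symmetric about zero when SIBO does nothing. Random allocation of the two sextants would make a standing difference between them equally likely to fall in either direction. The plan's rules do not.

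The SIBO sextant is not biopsied at baseline, and no unstented sextant is biopsied at Day 21. The planned tissue data therefore cannot separate a systematic sextant difference from a SIBO effect, and more subjects would only make such a difference more significant. The plaque change used in 2c and 2d has the same structure. The full-mouth clinical indices do not: they are repeated at visits 2 to 5 and can be compared within one sextant.

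**Working it through.** **Inputs from the documents (7.3.1, 11.2, 11.3).** 36 enrolled per group; 10% dropout, so 36 × 0.90 = 32.4, about 32 per group and 64 in all (7.3.1 counts 128 biopsies = 64 × 2); SD 0.25; intra-subject correlation 0.40; alpha 0.05, taken as two-sided.

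**SD of the paired change.** 0.25 × √(2 × (1 − 0.40)) = 0.274.

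**The plan's own figure.** Section 11.2 gives at least 80% power for a between-group difference in change of 0.40. With SD 0.274 and 32 per group, the 80% detectable difference is (1.96 + 0.84) × 0.274 × √(2/32) = 0.19. The statement is true but the figure is about twice what the inputs give. It does not bear on the sextant question, for which the plan has no figure.

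**Assumed input.** No side, arch or sextant difference in AIM2 or IFI16 is given. A shift of k = 0.1, 0.2 or 0.3 SD of the paired change is assumed, that is 0.03, 0.05 or 0.08 on the AIM2 scale.

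**Signed-rank rejection rate with no SIBO effect** (simulation, normal differences, two-sided 5%; repeat runs agree within about one point):

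| Shift | 64 pairs, all shifted | 32 pairs, all shifted | 64 pairs, half shifted |
|---|---|---|---|
| 0.1 SD | 12% | 8% | 7% |
| 0.2 SD | 33% | 18% | 11% |
| 0.3 SD | 64% | 37% | 21% |

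The first two columns are the worst case. In the last, half the pairs carry no contrast, as when the baseline biopsy comes from the other right posterior sextant. As a consistency check, half the pairs shifted by 0.2 SD has the same mean shift as all pairs shifted by 0.1 SD, and the rates agree (11% and 12%).

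**Randomised sextants.** Each difference becomes its error plus or minus d with equal chance, which is symmetric about zero. For d = 0.05, 0.10, 0.15 and 0.20 on the AIM2 scale, 32 pairs and all pairs shifted, the rate is 16%, 51%, 85% and 97% under the fixed rule and 4.6%, 5.3%, 4.8% and 5.0% when randomised. These rates assume no bias in the choice of papilla.

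**Between groups (1c, 1d), rank sum test, fixed rule.** If d is the same in both groups it cancels and the rate stays at about 5%. If d exists only in severe periodontitis, the rate is 11%, 30%, 54% and 78% for the same four values.

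**What randomising leaves.** With d = 0 and sextants randomised, choosing the highest-GI papilla at visit 5 against an unselected one at baseline biases the change by +0.02 to +0.12. This assumes 2 to 4 candidate sites and a GI-expression correlation of 0.2 to 0.6. The signed-rank rate with 32 pairs is then 7% to 69%.

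**Variance cost.** Unmodelled, the offset inflates the SD by √(1 + k²): at k = 0.3, √1.09 = 1.044, about 4%. At d = 0.05 and 0.10, rank sum power for a between-group difference of 0.20 falls from about 80% to 79% and 76%.

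**The case against.** The other side has a substantial case.

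- **The right side is a default.** A reader might infer that the stent always sits on the right and the baseline biopsy on the left. The documents do not support that. Section 6.2 has a dentition exception and allows either arch, and the baseline site need only be in a different sextant, which may be the other right one. An arch contrast can also run in either direction across subjects. This stands, and it is why the all-shifted figures are a worst case.
- **Not every difference biases.** A reader might infer that any standing difference counts as SIBO change. Differences that vary in direction between subjects only add noise; the difference has to be systematic.
- **The primary objective is largely protected.** A reader might infer that the main comparison fails. Objective 1 in section 3.1 compares the groups, and a difference common to both cancels there. However, section 11.1 also lists 1a and 1b as primary hypotheses, and they have no such protection.
- **No evidence of a difference.** Nothing in the documents gives a sextant difference in AIM2 or IFI16 or suggests that one exists. This stands: the sizes are illustrations.
- **Randomising is neither free nor sufficient.** A reader might infer that it restores the 5% level at no cost. It does not while the baseline papilla is the examiner's choice and the visit 5 papilla has the highest GI. Section 6.2 also wants stent teeth without a significant diastema, which 5.1 does not require, so some eligible subjects may have only one sextant suitable for a stent.

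These points limit the concern and change the fix. They do not alter the fact that sextant is tied to visit by non-random rules with no planned adjustment.

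**Conclusion.** The concern holds in limited form. Sextant is tied to visit by a right-side default and an examiner's choice. A systematic sextant difference is therefore inseparable from SIBO change in 1a and 1b and in the plaque change. It reaches 1c and 1d only if it differs between healthy and severe periodontitis.

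The size is unknown. Under assumed shifts of 0.1 to 0.3 SD, false positives with 64 pairs run from about 12% to 64% if every pair is shifted, and from about 7% to 21% if half are. These figures rest on normal differences and the plan's SD and correlation. They show how exposed the test is and are not evidence that a difference exists. This is a cheap improvement to the design; the between-group comparison is not shown to be invalid.

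**What to change.** 1. **Name the sextants first (6.1).** At Visit 1, before the impression, the examiner names two eligible posterior sextants, both suitable for a stent.
2. **Randomise (6.1, 6.2).** A prepared list, stratified by group, assigns one to the baseline biopsy and the other to the stent, replacing the right-side default. Subjects with only one stent-suitable sextant are assigned by necessity and flagged.
3. **Use one papilla-selection rule in both sextants.** For example, name the candidate papilla in each before allocation. Reconcile 6.1 (examiner's choice), 6.5 (highest GI) and Appendix II (provider determines). Without this step the selection bias shown above remains.
4. **Record and analyse (11.3).** Record side and arch for both samples. Adjust for allocation or examine it in a sensitivity analysis.
5. **Reconcile the extent of the model.** Section 2.3.1 describes two sextants without oral hygiene, while 7.1 describes one. The allocation wording needs a single statement.

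Cost: protocol wording and a short list, with no extra visit, biopsy or staff. Allocation must be set and recorded at Visit 1, and the stent side can no longer be assumed. If allocation is not modelled, a fixed offset becomes extra variance, up to about 4% in SD at 0.3 SD. If enrolment is too advanced to change, record and report both sextants and qualify the conclusions on 1a and 1b.
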